3.0 Institutional Experience and Rationale for Proposal

From January 1987 through July of 1998, nine patients underwent autologous bone marrow transplant for AML in first remission using the conditioning regimen consisting of busulfan and VP-16. Four of these nine patients are in remission now for more than 10 years, one patient died a toxic death during the neutropenic phase, there were no other unexpected toxicities.

Between March of 1989 and November 1993, the conditioning regimen was changed to FTBI 1200cGy/VP-16 60mg/kg and Cyclophosphamide 75mg/kg. We intended to transplant 60 adult patients with AML in first remission. All 60 patients underwent consolidation chemotherapy with high dose Ara-C (HD Ara-C) 3 gm/m² 8-12 doses. Following this consolidation treatment, bone marrow was harvested and cryopreserved. Ten patients relapsed prior to being transplanted. 44 patients underwent ABMT with a median follow-up time of 37 months. The cumulative probability of disease free survival at 24 months in the intent to treat group, is 49 percent and in those actually undergoing ABMT was 61%. The probability of relapse was 44% and 33% for the intent to treat and autologous BMT patients, respectively.

In an effort to try and improve on these results Idarubicin was added to high dose ara-c as part of the consolidation regimen and interleukin-2 was added to post BMT therapy to try and decrease the relapse rate. From August 1994 to the present time 58 patients have been evaluated with the intent to proceeding to an autologous stem cell transplant. For the intent to treat group the cumulative probability of disease free survival at three years is 67% and relapse rate 31%. For the 50 patients actually undergoing autologous stem cell transplant the cumulative probability of disease free survival at three years is 72% and their relapse probability is 27%.

Rev 5/15/01

Patients with good risk cytogenetics t (8;21) or INV 16 or t (16;16) have been shown to have improved DFS when treated with repeated cycles of high dose Ara-C alone.^{31,32} At City of Hope fifty six patients were treated with high dose Ara-C/idarubicin consolidation treatment with hematological recovery as follows:

ANC >500/ μ l median of 26 days [range 17,62]
ANC >1000/ μ l median of 27 days [range 18,65]
Untransfused platelets >20,000/ μ l median of 37 days [range 19,62]

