Due to the long hematological recovery and no literature evidence for adding idarubicin to the consolidation treatment, the protocol will be amended to omit idarubicin for patients with good risk cytogenetics.

At City of Hope between 8/92 and 10/98 61 patients were entered on a phase I study of escalating doses of busulfan in combination with TBI and VP-16 in patients with advanced hematological malignancies in an effort to try and improve the outcome of allogeneic bone marrow transplant in these poor risk patients. The MTD was defined at 11 mg/kg of busulfan in combination with FTBI 1200 cGy and VP-16 60mg/kg. The median AUC was 892 μ M*min (460-1267) for this group of patients. With a median follow up of 11.5 months, the disease free survival is 32%, and the probability of relapse is 40%. The only variable predictive of an improved disease free survival + relapse was Busulfan dose of 7-8mg/kg. An AUC of 700-950 μ M*min demonstrated a trend to a decreased relapse rate and improved DFS.

Allogeneic and autologous BMT studies performed in approximately 100 patients the I/V formulation has been shown to have more predictable pharmacokinetic properties than the oral preparation resulting in a better toxicity profile.⁽²⁶⁻²⁸⁾

Relapse is still the major reason for failure for BMT. In an attempt to try and decrease the relapse rate post autologous stem cell transplant we plan to substitute intravenous busulfan for cyclophosphamide in the conditioning regimen.

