Autologous PSC Reinfusion: Side effects from the bone marrow and peripheral stem cell infusion should be minimal. Volume overload may be seen, but can be managed with diuretics. Fevers and chills may occasionally be encountered. At the University of Nebraska at least two patients developed acute abdominal pain of unknown cause during their marrow infusions. The pain was managed with narcotic analgesics and resolved spontaneously. The lysis of frozen erythrocytes may be associated with hemoglobinuria. Patients will have positive tests for blood in the urine, but no erythrocytes will be found in the sediment. At the University of Nebraska three patients developed acute renal failure after autologous bone marrow infusion. This problem was presumed to be due to hemoglobinuria and was no longer seen after red blood cells were removed from the marrow prior to cryopreservation. This is not expected to be a problem since we will also be removing the red cells with Ficoll-Hypaque. DMSO will be infused along with the bone marrow. It is excreted through the lungs and its characteristic odor may be noticeable for a few days after marrow infusion.

8.0 STATISTICAL CONSIDERATIONS:

8.1 Primary and Secondary Endpoints: The primary endpoints of this Phase II study are to evaluate the toxicity and efficacy of FTBI/VP-16 and targeted Busulfan dosage for AUC 700-900 as a preparative regimen for autologous BMT with primed peripheral stem cells following consolidation therapy with high dose Ara-c and idarubicin or high dose Ara-c alone in patients with AML in first complete remission (CR). Complete remission will be defined as neutrophils >1500/ml and platelets >100,000. Efficacy will be estimated as 2 and 5 year disease-free survival (DFS). The role of IL-2 following autologous BMT will also be evaluated based on feasibility of administration and ability to tolerate IL-2. The effect of cytogenetics, WBC at presentation, AUC of Busulfan and number of courses of induction therapy to achieve remission will be evaluated as possible prognostic factors for relapse, DFS, and overall survival.

8.2 Sample Size Estimation and Length of Accrual: A total of 50 patients with AML in first CR and less than \leq 60 years old will be accrued to this trial, so that in estimating the engraftment and relapse rates the maximum standard error will be 0.07. We expect to accrue approximately 10-12 patients per year so that this trial will require 4-5 years for completion.

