8.3 Statistical Analyses: The rate of engraftment and median time to engraftment will be estimated, defined as time to ANC>500 and platelets > 20,000.

The Kaplan-Meier method will be used to estimate time to relapse, DFS, and overall survival, and 95% confidence intervals will be calculated using Greenwold's variance. All patients receiving HD Ara-c and Idarubicin consolidation will be included in the analysis for intent-to-treat with autologous BMT. For overall survival, failure time will be calculated from the day of first consolidation treatment to the day of death due to any cause for those patients who fail. For DFS, the failure time will be calculated from the day of first treatment to the day of disease relapse or death due to any cause. For patients who remain alive and well at the time of analysis, the survival time will be censored as of the date of last contact.

A further analysis of time to relapse, DFS and overall survival will be carried out for the subset of patients who go on to autologous BMT, with survival estimates calculated from the day of transplant. The Cox proportional hazard regression model will be used to analyze possible prognostic factors for relapse, DFS and overall survival.

8.4 Early Stopping Rules: If at any time the severe treatment related complication rate (e.g. severe VOD, interstitial pneumonia, neurotoxicity at day 100 post ABMT), exceeds 10%, with a high probability (i.e. 95%) then further accrual to the trial will be terminated. Similarly if with a high probability (95%) the regimen related mortality at day 100 post ABMT exceeds 10% the trial will be terminated. This would occur if the following numbers of events have been observed, monitoring after every set of 10 patients it accrued:

Number of Patients Accrued	Number of Adverse Events Leading to Early Termination
10	4
20	5
30	7
40	8

Rev. 5/7/01

We will stop accrual of good risk cytogenetic patients on the study if the good risk cytogenetic patients demonstrate excess relapse. Based on previous COH experience, good risk cytogenetic patients have a relapse rate of 13%. The study will close if the lower bound of an estimate of the true rate of relapse exceeds 15% for the subgroup. Evidence of relapse will be taken as the lower limit associated with an exact 95% one-sided confidence interval for proportions. Table 1 below shows the critical points for early stopping of accrual.

Table 1: Critical points for early stopping for relapse

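### Section 8.3 estimates time to relapse by Kaplan-Meier alone and does not say how deaths in remission are handled; if they are censored, 1-KM is at or slightly above the proportion who relapse

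*Combined protocol and SAP*

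**What the plan says.** Section 8.3 names one method for three outcomes: "The Kaplan-Meier method will be used to estimate time to relapse, DFS, and overall survival". For their intervals, "95% confidence intervals will be calculated using Greenwold's variance".

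It then gives the failure time for overall survival (first consolidation treatment to death from any cause) and for DFS (first treatment "to the day of disease relapse or death due to any cause"). No such sentence follows for time to relapse. The only censoring rule covers patients who are alive and well, so it does not cover a patient who died in remission.

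The same three outcomes are analysed again in those who reach transplant: "A further analysis of time to relapse, DFS and overall survival will be carried out for the subset of patients", with survival estimates counted from the day of transplant. The document nowhere mentions competing risks or cumulative incidence.

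**The concern.** A patient who dies in remission can no longer relapse. Kaplan-Meier with that patient censored estimates what relapse would be if such deaths were removed, assuming the two risks are independent. It does not estimate the proportion of treated patients who relapse, and it cannot fall below that proportion. If such patients are instead kept in the risk set as event-free, complete follow-up gives the cumulative incidence, which is a different figure. Two analysts could follow 8.3 and report different relapse probabilities.

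The relapse figure carries weight in the rationale. Section 3.0 says: "In an attempt to try and decrease the relapse rate post autologous stem cell transplant we plan to substitute intravenous busulfan". Section 8.2 justifies 50 patients so that "in estimating the engraftment and relapse rates the maximum standard error will be 0.07". Section 3.0 reports relapse for both of the FTBI-based series, so the new figure will be compared with them. Any excess grows with non-relapse mortality, which is not yet known for this regimen.

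**Working it through.** **The plan's own figure.** The largest binomial standard error with 50 patients is sqrt(0.5 × 0.5 / 50) = 0.0707, which reproduces the 0.07 in Section 8.2. This is the standard error of a simple proportion; 8.3 gives no separate estimator for that proportion.

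**Inputs (Section 3.0).** Recent intent-to-treat series, 58 patients: 3-year DFS 67%, relapse 31%. Recent transplanted patients, 50: 3-year DFS 72%, relapse 27%.

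**Assumptions.** The relapse figure R is 1-KM with deaths in remission censored, and refers to the same three years as DFS.

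**Formulas.**
- Net non-relapse mortality: N = 1 − DFS/(1 − R).
- Cumulative incidence of relapse under proportional hazards: CIF = (1 − DFS) × ln(1 − R)/ln(DFS). Excess = R − CIF.
- Excess if every death in remission precedes every relapse: R × N.
- If the deaths follow the relapses, the excess approaches 0.

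**Recent intent-to-treat series.**
- N = 1 − 0.67/0.69 = 0.0290.
- CIF = 0.33 × ln(0.69)/ln(0.67) = 0.3058, so the excess is 0.42 points. A constant-hazard simulation of 2,000,000 patients gave 0.43.
- Deaths first: 0.31 × 0.0290 = 0.90 points.

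**Recent transplanted patients.**
- N = 1 − 0.72/0.73 = 0.0137.
- CIF = 0.28 × ln(0.73)/ln(0.72) = 0.2682, so the excess is 0.18 points.
- Deaths first: 0.27 × 0.0137 = 0.37 points.

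**Rounding.** The inputs are whole percents, and N is a small difference between them. Moving each by ±0.5 points:
- Intent-to-treat: N runs from 1.5% to 4.3%, and the excess from 0.22 (proportional hazards, lowest) to 1.32 points (deaths first, highest: 0.305 × 0.0432).
- Transplanted: the excess runs from 0 to 0.72 points (highest: 0.265 × 0.0272).

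**If the stated figures are already cumulative incidences (C).** Then 1-KM = 1 − DFS^(C/(1 − DFS)) under proportional hazards, or C/(1 − d) with deaths first, where d = 1 − DFS − C.
- Intent-to-treat: d = 0.02; 1-KM = 0.3135 or 0.3163; excess 0.35 to 0.63 points.
- Transplanted: d = 0.01; 1-KM = 0.2715 or 0.2727; excess 0.15 to 0.27 points.

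**Illustration at N = 10%** (the mortality threshold in Section 8.4, not an expected rate), with R = 31%:
- DFS = 0.69 × 0.90 = 0.621.
- CIF = 0.379 × ln(0.69)/ln(0.621) = 0.2952, so the excess is 1.48 points.
- Deaths first: 0.31 × 0.10 = 3.10 points.

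**Scale.** 0.9 points is 0.45 of a patient in 50, against a standard error of 7 points.

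**The case against.** The strongest reply is that nothing turns on this. Section 8.1 measures efficacy by 2- and 5-year DFS. DFS and overall survival count deaths as events. The 8.4 rules use counts of events, with exact binomial limits for relapse. An excess of less than one patient in 50 cannot be told from noise in a single-arm study of this size. All of that stands, and it is why this is a minor reporting point.

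A second reply is that the choice is one of estimand. If the rationale is better leukemia control, the censored estimate is a legitimate target when the two risks are independent, and a toxic regimen can lower the cumulative incidence simply because patients die first. That also stands. It is a reason to keep 1-KM and to show non-relapse mortality beside the cumulative incidence, but not a reason to leave the rule unstated.

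Some stronger readings are tempting, but the documents do not support them:
- **That Greenwood's variance is wrong.** Section 8.3 attaches it to Kaplan-Meier, where it belongs. A different variance is needed only if a cumulative incidence is added.
- **That 0.4 to 0.9 points describes the institution's recent experience as a whole.** It holds for the intent-to-treat series only, and its upper end needs every death in remission to precede every relapse.
- **That the excess is several points.** Applying the same formulas to the 1989 to 1993 series gives 1.4 to 3.0 points (transplanted, 61% DFS and 33% relapse) and 2.5 to 5.5 (intent-to-treat, 49% and 44%). However, Section 3.0 gives no time point for those relapse figures, and neither their estimator nor their deaths in remission are stated. Converting the 44% into a count of relapses, to allow for the ten before transplant, would treat an estimate of unknown type as a crude proportion.
- **That the Cox model for relapse is invalid.** With deaths censored it is a valid cause-specific hazard model.

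**Conclusion.** The gap is real and small. Section 8.3 leaves deaths in remission without a rule in both relapse analyses. Censoring them is an inference, drawn from the separate listing of relapse and DFS; the text does not say so. Under that inference 1-KM is at or above the proportion who relapse. The size depends on the cohort and on the timing of deaths, within the ranges shown in the working, and those ranges rest on the Section 3.0 relapse figures being 1-KM at the same time point as DFS. Every range for the recent series, and the 10% illustration, is well under the planned standard error.

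A reader might infer that the trial's efficacy result or its stopping decisions are biased. They are not: none uses the Kaplan-Meier relapse estimate. The case for acting is that the excess runs in one direction, does not shrink with more patients, and costs little to remove.

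**What to change.** In Section 8.3:

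1. Define the relapse event and its start date for both analyses (all patients and the transplanted subset), and say how a death in remission is treated.
2. Report the cumulative incidence of relapse with death in remission as a competing event, always beside the cumulative incidence of non-relapse mortality. Give each a variance suited to that estimator (Aalen or delta-method).
3. Keep 1-KM with Greenwood intervals as a secondary figure for comparison with the historical series, and note that the documents do not state which estimator those series used.

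The cost is a few sentences and one extra analysis in standard software. No new data are needed, since DFS and overall survival already require the dates of relapse and death. The downside is a second relapse figure, which has to be labelled clearly so that the two are not confused.

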1.0 OBJECTIVES

- a. To evaluate the efficacy and toxicity of fractionated total body irradiation (FTBI) in combination with busulfan (BU) dosage targeted to AUC 700-900 and VP-16 followed by post-BMT interleukin-2 (IL-2) as a preparative regimen for autologous BMT for patients with AML in 1st CR.
- b. To estimate the long term disease free survival for patients \leq 60 years of age with AML in first remission receiving an autologous BMT utilizing primed peripheral stem cells following consolidation therapy with high dose ara-c and Idarubicin or high dose Ara-c alone.
- c. To further evaluate the effect of prognostic factors e.g. cytogenetics, WBC at presentation, number of courses of induction therapy to enter remission on the outcome of autologous BMT and AUC of Busulfan.

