6.2 Consolidation Chemotherapy

6.21 Patients who have received consolidation treatment prior to coming to City of Hope will be evaluated to determine how many doses of HD Ara-c and anthracycline they have received. Patients who have received more than 200mg/m² of anthracycline will not receive idarubicin. Patients who have received 8 or more doses of HD Ara-c will have GCSF primed cells collected. Patients who have had < 8 doses of HD Ara-C will receive additional HD Ara-C not to exceed 12 doses [36grams/m²].

6.22 Patients who have received no consolidation treatment will follow the following treatment plan:

Revised 8/7/00

a). Beginning 4 hours prior to starting Ara-C all patients will be adequately hydrated. All patients will require anti-emetics to control nausea and vomiting. Patients will undergo a neurological assessment prior to each dose of Ara-C for evaluation of cerebellar symptoms.

Revised 8/7/00

b) Patients will receive Ara-C 3 gm/m² IV over 3 hours every 12 hours for a total of 8 doses. (Day 1-4). Patients age 55 to 60 will receive 2gm/m² of Ara-C.

Revised 5/4/01

c) Idarubicin 12 mg/m² will be given by slow intravenous infusion (5-10 minutes) after Ara-C dose 1, 3, 5. (Day 1-3). Patients with good risk cytogenetics (t 8;21) or inv 16 or (t 16;16) will not receive the idarubicin.

Revised 3/11/02

d) GCSF 10 µg/kg IV or subcutaneously in 2 divided doses will be started 7 days after Ara-C completed and continued until peripheral stem cell collections are completed.

e) Once patients' WBC >5000/µl peripheral stem cells will be collected with the goal collecting 3 x 10⁶/kg CD34 cells (target 3-5 x 10⁶/kg). If stem cell collections are poor the stem cell collection should then be delayed until the platelet count recovers to > 50,000. The G-CSF

dose can be increased to 16 mcg/kg/day subcutaneously in 2 divided doses [or I/V depending on transplant center standard protocol.

Revised 8/7/00

f) CBC, platelet count daily, (differentials per MD discretion), comprehensive metabolic panel plus uric acid, LDH, phosphorous and cholesterol, Mg⁺⁺ are drawn daily during chemotherapy then every Monday, Wednesday, Friday during consolidation therapy.

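### The intent-to-treat set in section 8.3 names only patients given Ara-C plus idarubicin, so an Ara-C-alone patient who fails before transplant enters neither Kaplan-Meier analysis

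*Combined protocol and SAP*

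**What the plan says.** Section 8.3 plans Kaplan-Meier estimates of time to relapse, disease-free survival (DFS) and overall survival on two sets.

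- **From consolidation.** "All patients receiving HD Ara-c and Idarubicin consolidation will be included in the analysis for intent-to-treat with autologous BMT". This is the only sentence that says who belongs to this set.
- **From transplant.** A further analysis is "carried out for the subset of patients who go on to autologous BMT, with survival estimates calculated from the day of transplant". It carries no condition on idarubicin.

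Elsewhere the study population is wider. Objective 1.0(b) concerns autologous transplant "following consolidation therapy with high dose ara-c and Idarubicin or high dose Ara-c alone". Section 8.1 sets the primary endpoints for the regimen given "following consolidation therapy with high dose Ara-c and idarubicin or high dose Ara-c alone", and measures efficacy as 2- and 5-year DFS. Section 6.22(c) creates the Ara-C-alone group: "Patients with good risk cytogenetics (t 8;21) or inv 16 or (t 16;16) will not receive the idarubicin". Section 3.0 gives the reason, slow haematological recovery and no literature support for the drug at this step, and says that "the protocol will be amended to omit idarubicin for patients with good risk cytogenetics".

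Sections 5.0(e) and 5.0(f) set aside for separate evaluation patients consolidated before arrival and patients in remission for more than 6 months. They say nothing about Ara-C-alone patients consolidated on protocol.

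**The concern.** The protocol creates a group, places it in the primary-endpoint population in 8.1, and then does not name it in the one sentence that defines the intent-to-treat set. Taken at its word, that sentence leaves out good-risk patients enrolled after the amendment. It also leaves out anyone else who receives no idarubicin at all, for example through the 100% reduction for bilirubin in section 6.3.

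The from-consolidation estimate is the one that counts failures before transplant, and the plan's own history shows that these are not rare. Of the 60-patient cohort, section 3.0 reports: "Ten patients relapsed prior to being transplanted. 44 patients underwent ABMT with a median follow-up time of 37 months". If the set can be built in two ways, with and without the Ara-C-alone patients, the choice could be made after outcomes are known. Fixing the set in advance is meant to prevent that.

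**Working it through.** **1. Who is in which analysis, read literally**

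| Patient | From consolidation | From transplant |
|---|---|---|
| Ara-C + idarubicin, transplanted | yes | yes |
| Ara-C + idarubicin, fails before transplant | yes | no |
| Ara-C alone, transplanted | no | yes |
| Ara-C alone, fails before transplant | **no** | **no** |

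Nothing elsewhere fills the last row. Sections 5.0(e) and (f) concern other patients. Table 1 in section 8.4 counts relapses in good-risk patients for stopping and gives no DFS or survival estimate.

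**2. The plan's precision figure**

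Section 8.2 states a maximum standard error (SE) of 0.07 for engraftment and relapse rates with 50 patients. Maximum SE = √(0.25/n), and √(0.25/50) = 0.0707, so the figure reproduces.

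**3. Precision if k Ara-C-alone patients are left out**

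The documents do not give k; 5, 10 and 15 are assumed.

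| k | n = 50 − k | √(0.25/n) |
|---|---|---|
| 0 | 50 | 0.0707 |
| 5 | 45 | 0.0745 |
| 10 | 40 | 0.0791 |
| 15 | 35 | 0.0845 |

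**4. Patients in neither analysis**

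Section 3.0 gives two historical fractions not transplanted.

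- First cohort: (60 − 44)/60 = 16/60 = 0.267. Ten of the 60 (0.167) relapsed before transplant.
- Second cohort, in which "58 patients have been evaluated with the intent to proceeding to an autologous stem cell transplant" and 50 were transplanted: (58 − 50)/58 = 8/58 = 0.138. The reasons for these 8 are not given.

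Multiplying each fraction by k:

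| k | × 0.138 | × 0.267 |
|---|---|---|
| 5 | 0.69 | 1.33 |
| 10 | 1.38 | 2.67 |
| 15 | 2.07 | 4.00 |

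Neither cohort was restricted to good-risk patients, so these are only a guide.

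**5. Possible shift in the relapse estimate**

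Let s = k/50, let g be the relapse rate in the omitted patients, and let the overall rate be 0.31 (the 58-patient intent-to-treat cohort in section 3.0, which had different conditioning). The literal set then shows (0.31 − s·g)/(1 − s), so the shift is s(0.31 − g)/(1 − s).

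| k | s | g = 0.13 (section 8.4) | g = 0.31 | g at the Table 1 limit |
|---|---|---|---|---|
| 5 | 0.1 | +2.00 points | 0 | 3/5 = 0.60: −3.22 |
| 10 | 0.2 | +4.50 points | 0 | 4/10 = 0.40: −2.25 |
| 15 | 0.3 | +7.71 points | 0 | 6/15 = 0.40: −3.86 |

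Example: k = 15, g = 0.13 gives (0.31 − 0.039)/0.7 = 0.3871, which is 7.71 points above 0.31. The sign depends on g, which is what the trial is there to learn. No shift in DFS was computed.

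**The case against.** The strongest reply is that the sentence is incomplete and does not truly exclude anyone. It says who will be included and does not say only. Section 8.1 names Ara-C alone explicitly. Objective 1.0(c) and section 8.1 want cytogenetics examined as a prognostic factor, which makes little sense from consolidation if the good-risk group is missing. A sensible analyst would probably include these patients. That stands as a guess about practice. It does not supply a rule, because no sentence assigns them to the set.

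Other points have some force:

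- Objective 1.0(b) speaks of patients receiving a transplant, so the from-transplant analysis could answer it. Section 8.1 is the firmer ground for the conflict.
- Relapses before transplant in good-risk patients are still counted for stopping in Table 1, by enrolment. This limits the harm but gives no survival estimate.
- For good-risk patients, omission follows a baseline characteristic and not behaviour after enrolment, so the charge that the set is not intent-to-treat is milder for them. It applies fully to patients who lose idarubicin under section 6.3. The proposed wording also requires that treatment has started, but that start is where follow-up begins.
- Section 8.2 does not tie the 0.07 to this set, engraftment is assessed only after transplant, and separate evaluation under 5.0(e) and (f) may leave fewer than 50 in any case. At 31% relapse, √(0.31 × 0.69/n) is 0.065, 0.069, 0.073 and 0.078 for n = 50, 45, 40 and 35, so omitting 5 patients would still meet 0.07.
- The relapse shifts rest on assumed inputs. The 13% has no stated regimen, time point or denominator, and the largest shift requires 38.7% relapse in the idarubicin group.

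These points limit the size of the problem and leave the gap itself in place.

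**Conclusion.** The concern holds: section 8.3 is wrong as written. Its only membership rule for the from-consolidation set omits a group that section 8.1 includes and section 6.22(c) creates. The likely cause is wording not updated when idarubicin was dropped for good-risk patients. Revision marks from May 2001 stand beside the change in sections 3.0, 6.22(c) and 8.4. That cause is an inference; the conflict is in the text.

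The size is moderate and partly unknown. With 5 to 15 Ara-C-alone patients assumed, about 0.7 to 4 would be in neither analysis and the worst-case SE would be 0.075 to 0.085. The illustrative relapse shift runs from −3.9 to +7.7 points, so no direction of bias can be claimed. No test or stopping rule uses this set, and transplanted Ara-C-alone patients remain in the from-transplant analysis. The point should be fixed, but it does not threaten the trial as a whole.

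**What to change.** Replace the sentence in section 8.3 with: *All patients who start protocol consolidation with HD Ara-C, with or without idarubicin, will be included in the intent-to-treat analysis, whether or not they are transplanted.* Keep the patients described in 5.0(e) and 5.0(f) evaluated separately, as section 5.0 already provides.

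The cost is one sentence. It needs no extra patients or data and changes no treatment.
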